## 11. Non-significant Risk Determination

In accordance with the definition of "Significant Risk Device" provided in the U.S. Code of Federal Regulations 21 CFR 812.3, the study device to be used in this research study has been determined to be a Non-Significant Risk (NSR) device based on the following:

- a) It is not an implant
- b) It is not purported or represented to be for use in supporting or sustaining human life
  - and do not present a potential for serious risk to the health, safety or welfare of a subject
- c) It is not for a use of substantial importance in diagnosing, curing, mitigating, or treating disease or otherwise preventing impairment of human health
- d) Use of the device poses no risk to the health, safety, or welfare of a subject

## 12. Device Description

The device to be used in this study is an FDA cleared device [510(k), K161043] for percutaneous treatment of facial wrinkles and improvement in appearance of cellulite in subjects with Fitzpatrick skin types I-III. The Profound System (Image 1) consists of a reusable console which contains a radiofrequency (RF) generator and graphical user interface, two re-usable treatment handpieces, and two disposable, single use, sterile electrode cartridges.

Image 1: Profound System

[figure not shown]

The Profound system has a powered console with a graphical user interface for adjustment of treatment parameters. The RF frequency of the Profound System is 460 +/- 5kHz. Bipolar RF travels from the RF generator, through the electrodes, into the dermal layers beneath the surface of the skin. The dimensions of the treatment area vary depending on the handpiece (Image 2). The 25° handpiece has 5 independent channels and covers a treatment area of 14mm. The 75° handpiece consists of 7 independent channels and covers a treatment area of 20mm. Specifically, the 25° Dermal handpiece and cartridge are used for the percutaneous treatment of facial wrinkles, while the 75° SubQ handpiece is used to improve the appearance of cellulite (Image 3). Additionally, the Profound System provides real-time temperature feedback through temperature sensors. For this study, only the 25° handpiece will be utilized.

Image 2: Dermal Handpiece

- Treats the Dermal layer, between 1 – 2 mm
- Single-use cartridge with 5 pairs of micro-needles
- Cold plate for epidermal protection

### 13. Potential Risks

#### ***Blistering, burning, and infection: (Rare)***

A crust, blister or superficial wound can occur at the treatment area. The risk of infection will be minimized by proper wound care.

#### ***Bruising: (Rare)***

A mild bruising may occur at the treatment area as a result of radiofrequency exposure. This is usually transient and resolves in a few hours to few days.

#### ***Transient edema and/or erythema: (Occasionally)***

May develop within the irradiated areas but are usually temporary and fade within 24-72 hours.

#### ***Pigmentary changes: (Rare)***

Radiofrequency exposure can cause pigmentary changes such as hyper- (and hypopigmentation. Although this is usually temporary, it may be permanent on rare occasions. Sun avoidance and/or the use of a total sun block (SPF 30 or higher) will help minimize the intensity and duration of any pigmentary changes.

#### ***Scarring: (Rare)***

As with any form of energy exposure, there is a small risk of scarring. However, this is minimized by proper technique and wound care.

#### ***Allergic Reaction: (Rare)***

There is a possibility of an allergic or toxic reaction to anesthesia used to numb the areas. Subjects will be questioned with regard to any history of allergies and carefully monitored for signs of allergic reaction.

#### ***Biopsy***

Risks associated with biopsy include: 1) scarring - a small risk of scarring, which can be mitigated by proper technique and wound care; 2) allergic reaction - there is a possibility of an allergic or toxic reaction to anesthesia used to numb the areas. Subjects will be questioned with regard to any history of allergies and carefully monitored for signs of allergic reaction.

#### ***Photography***

The subject may be uncomfortable with sitting still for an extended period of time or from turning his/her body in various positions. Subjects may be sensitive to the bright and repeating flashes from the camera, which can sometimes cause headaches, irritation of the eyes, discomfort, after effects such as seeing spots, and in rare cases, could stimulate a migraine headache or epileptic seizure.

Photographs include a risk of identification, as these will be full face photos. Privacy will be protected to the greatest extent possible. Photos will only be identified by a unique subject identification number that contains no personal identifying information. All photos will be stored on a password secure drive, with only access by research personnel. For research purposes, photos may be used in scientific publications.

#### ***Noninvasive procedures (exploratory)***

- Biox Aquaflux will be used to measure transepidermal water loss (TEWL) measurements which evaluate barrier function of the skin epidermal layer to determine progress of epidermal healing after treatment. The standard time for TEWL measurements should take approximately 5 minutes.
- Vivosight, an Optical coherence tomography (OCT) device, will be used to noninvasively gather topographical and histologic images of pre- and post-treated skin. The standard time for OCT should take approximately 5-10 minutes.
- The BTC 2000 will be used to measure skin laxity, viscoelastic deformation, stiffness, energy absorption, elasticity, and deformation

values of skin. The standard time for BTC 2000 should take approximately 5 minutes.

All these test are considered noninvasive and no risks are anticipated with these tests.

#### 14. Potential Benefits

Subjects may benefit by having an overall improvement in submental skin laxity or an overall improvement in skin tone or texture in the treated areas, but this is not guaranteed. There may be a benefit to the medical community by demonstrating the safety and effectiveness of a new technology in the management of skin laxity of the submentum. This technology may have advantages over existing technologies currently in use (lasers, ultrasound, etc.) because of its combination of bipolar fractional radiofrequency and microneedling technology. This technology may lead to better clinical outcomes for an understudied area.

#### 15. Adverse Events

##### 15.1 Definitions

###### Adverse Event

An adverse event is any untoward medical occurrence, unintended disease or injury, or untoward clinical signs (including abnormal laboratory findings) in subjects, users or other persons, whether or not related to the investigational medical device.

###### Unanticipated Adverse Device Effect

An unanticipated adverse device effect (UADE) is any serious adverse effect (defined below) on health or safety, any life-threatening problem or death caused by, or associated with a device, if that effect, problem, or death was not previously identified in nature, severity, or degree of incidence in the protocol; or any other unanticipated serious problem associated with a device that relates to the rights, safety, or welfare of subjects.

A serious adverse event (SAE) is any adverse event that:

- a) led to death,
- b) resulted in life-threatening illness or injury
- c) resulted in permanent impairment of a body structure or body function
- d) resulted in in hospitalization or prolongation of existing hospitalization,
- e) resulted in medical or surgical intervention to prevent permanent impairment to body structure or body function, or
- f) led to fetal distress, fetal death, congenital abnormality or birth defect

## 15.2 Reporting

Adverse events, and unanticipated adverse device effects (UADE) are collected from the time of subject consent until the subject exits the study. A description of the adverse event or device event, date of onset, severity, action taken, relationship to study treatment and outcome are documented in the case report form.

The Investigator will submit to the reviewing IRB a report of any unanticipated adverse device effect (UADE) as soon as possible, but in no event later than 10 working days after the investigator first learns of the event (CFR 812.150(a)(1)).

## 16. Subject Safety and Data Monitoring

For this protocol, which involves the use of a non-significant risk device, the Investigator will be responsible for the conduct of the study including accrual, subject experience, attrition, patterns of expected adverse events and/or unexpected adverse events, any protocol deviations or violations, and any changes in the risk/benefit analysis.

Subjects will be asked about any adverse events throughout the study by the study staff. Subjects will be asked to contact the study staff if adverse events develop between visits. An unscheduled visit will be arranged so that the Investigator can clinically evaluate and photograph these findings. All subjects will be discontinued from the study if their problem remains unchanged/becomes worse. The Investigator can decide to stop the study if he/she believes that the participants' participation is no longer safe or if another treatment may be more helpful. The IRB or FDA may stop the research for the safety of the participants. These adverse events will be documented and reported as required for compliance with applicable regulations.

All study records and information will be identified by the subject number. All subject identifiers will be removed from all documents. The link between subject name and study ID number will be kept in separate password-protected files at the study site. Documents containing identifying information will be kept in locked files in the research staff's locked office. All electronic study data will be password protected with access limited to members of the research team. No direct identifying information will be shared with any outside entities, unless required by regulatory agencies (FDA and IRB). Electronic data (electronic data entry - Case Report Forms) if used will be password protected.

Photographs of the subject's face will be taken at Enrollment/Treatment and Follow-Up visits. These photographs will be identified by subject numbers. Subject confidentiality will be protected to the greatest extent possible. Quantitative surface area assessments will be done on lateral 3D images taken at baseline and compared with 3D images obtained at all follow-up visits.

This study will be performed in accordance with Health Insurance Portability and Accountability Act. These guidelines will be followed specifically with regards to the privacy and confidentiality of subject care and study records. Personnel associated with Investigator's office and the governing Institutional Review Board, have the right to review the data, including photographs, collected during this study.

Personnel associated with Investigator's office and the governing Institutional Review Board have the right to review the data, including photographs, collected during this study.

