### 3. Study Design

This is a single-center, unblinded, non-randomized, non-controlled study designed to follow a total of up to 15 qualified and consenting subjects to receive one bipolar fractional radiofrequency microneedling treatment under an IRB approved protocol. The Principal Investigator(s) have been selected based on his expertise, qualifications (credentials, training, and medical specialty), subject access, previous clinical research, facilities, and interest in this particular field of research.

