#### 7.4 Follow-up Visits (Visits 3 and 4)

At a minimum, all subjects will return for follow-up at 3 months (+/- 7 days) and 6 months (+/- 7 days) after treatment.

The following activities will be performed on all subjects during the follow-up visits:

- a) The physician or study staff will perform an examination of the skin of the treatment area.
  - All expected (e.g., edema, erythema) and unexpected (e.g., burn, blister) treatment local skin responses will be documented and graded at every visit
- b) Adverse Event Review
  - Query the subject regarding any change in health since enrollment into the study.

- Perform a detailed cutaneous exam of the treatment area, review and record any local adverse events related to cutaneous changes.

c) Collect an updated surgical history and record any change in concomitant medications or treatments.

d) Images will be obtained using the optical coherence tomography, BTC 2000, Bio Aquaflux, and/or high-resolution ultrasound, as was done previously.

e) The two small biopsies within the treatment area will be taken at each visit.

f) Take close-up and standard photography

g) Surface area assessments via the Vectra H2 3D Imaging System and Standup Vectra

These visits will take about 45 minutes – 1 hour.

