## 7.5 Additional, Unexpected Follow-Up Visits

If a potential adverse event is reported by the subject or identified during examination, the Investigator or study staff will schedule the subject for an Event Follow-up Visit within 24 hours. At this visit the Investigator or his designee will:

- a. Obtain a complete history of the event in question as well as conduct an examination of the subject and determine if the reported event qualifies as an Adverse Event. If the event is determined to be an Adverse Event, an Adverse Event (AE) case report form and Event Follow-up (EF) Visit case report form must be completed. One AE case report form should be used to track the history of an individual AE throughout the period of the study.
- b. Collect an updated medical and surgical history along with recording of concomitant medications or treatments.
- c. Take photographs of the subject with attention to the area in question.
- d. Render treatment for the event, if any, as determined by the medical judgment of the investigator.

Additional follow-up visits may also be required after the last scheduled visit to assess resolution of adverse events.

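### Section 16 removes subjects with unchanged or worsening adverse events from the study, and no passage says whether their safety follow-up and Month 6 assessments continue

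*Combined protocol and SAP*

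**What the plan says.** Section 16 describes an unscheduled visit at which the investigator evaluates and photographs an adverse event, and continues: "All subjects will be discontinued from the study if their problem remains unchanged/becomes worse". It gives no severity threshold and no interval over which a lack of change is judged. Removal is from the study, not only from treatment.

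Section 15.2 says that adverse events and unanticipated device effects "are collected from the time of subject consent until the subject exits the study". It lists what goes on the form, including that "relationship to study treatment and outcome are documented in the case report form".

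Other text points towards continued observation:

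- Section 7.4: "At a minimum, all subjects will return for follow-up at 3 months (+/- 7 days) and 6 months (+/- 7 days) after treatment".
- Section 7.5: "One AE case report form should be used to track the history of an individual AE throughout the period of the study". It adds: "Additional follow-up visits may also be required after the last scheduled visit to assess resolution of adverse events".
- Section 16 itself: "Subjects will be asked about any adverse events throughout the study by the study staff".
- Section 6, safety endpoint analysis: safety rests on the treatment visit and all follow-up evaluations.

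Section 3 plans for "up to 15 qualified and consenting subjects to receive one bipolar fractional radiofrequency microneedling treatment".

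**The concern.** In a study with repeated dosing, a rule that removes subjects with persistent events can limit further exposure. Here treatment is given once, on Day 0. A subject discontinued after that receives no less study treatment, but is observed less.

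The possible loss is informative, because the rule selects subjects by the course of their adverse event. Severity is part of the primary safety endpoint (Section 6.1.2). Section 15.1 also makes permanent impairment a criterion for a serious event, and whether a lasting event is permanent can be learned only by continuing to look. The safety result could therefore depend on which section the study staff apply.

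The ratings made only at Month 6 would lose the same subjects.

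**Working it through.** The plan gives no discontinuation rate and no derivation of the figure of 15, so there is no stated result to reproduce. The check is a comparison of the texts, followed by simple arithmetic on the sample size.

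**1. Which text governs a discontinued subject?**

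| Section | What it requires | Does it settle the matter? |
|---|---|---|
| 16 | Removal from the study if the event is unchanged or worse | Mandatory; silent on later data |
| 15.2 | Adverse event collection until exit; outcome recorded | Exit undefined; treating discontinuation as exit is a natural inference, not a stated rule |
| 7.4 | All subjects return at 3 and 6 months | No exception stated for discontinued subjects |
| 7.5 | Each event tracked during the study; later resolution visits possible | Permissive, tied to the last scheduled visit, silent on discontinued subjects |
| 8 | Visits at Months 3 and 6 | No early-termination visit |

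No section ranks these texts. Under Sections 16 and 15.2 read literally, collection stops at discontinuation. Under Section 7.4, it runs to Month 6.

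**2. What is at risk, by time of discontinuation?** There are two scheduled follow-up visits.

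- Before Month 3, which needs an event reported between visits: both scheduled visits, plus between-visit reporting.
- At the Month 3 visit: one of the two visits, plus between-visit reporting. The Month 3 imaging and skin-test readings can be kept, and Section 9 analyses every applicable post-baseline time point.
- In either case: the blinded lift rating, the blinded GAIS and the clinician GAIS. These are read only at Day 180 or Month 6 (Sections 2, 6.2, 8 and 10), so Month 3 data cannot replace them.

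**3. What is kept?** The event, its relatedness and its severity up to discontinuation (Sections 15.2 and 16).

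**4. Weight of each subject.** Share of those treated = k/n, where k is the number discontinued and n the number treated.

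- n = 15: 1/15 = 6.7%; 2/15 = 13.3%; 3/15 = 20.0%.
- Enrolment is capped at 15, so 6.7% is a minimum. With n = 12 (assumption), 1/12 = 8.3%. With n = 10 (assumption), 1/10 = 10.0%.

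**5. Would it arise at all?** Suppose each subject has probability p of meeting the rule (assumption; the plan gives none). The chance of at least one among 15 is 1 − (1 − p)^15:

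- p = 0.02: 1 − 0.98^15 = 26.1%
- p = 0.05: 1 − 0.95^15 = 53.7%
- p = 0.10: 1 − 0.90^15 = 79.4%

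**The case against.** The strongest reply is that Section 7.4 is a general schedule and Section 16 a specific exception, as in any protocol with a withdrawal rule. Section 7.5 provides for tracking and resolution visits, and Section 15.2 asks for an outcome. On that view sensible staff would follow these subjects anyway. The primary safety endpoint lists incidence, severity and relatedness, not duration or outcome. Section 13 describes bruising, edema and erythema as usually temporary, and labels scarring and pigmentary change as rare, so few discontinuations are likely in a small exploratory study.

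Much of this limits the size of the point. The equation of discontinuation with exit is an inference, and few subjects may be affected. It does not remove the gap: the resolution visits are optional, and if continued follow-up is intended, the text does not say so.

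Four stronger readings are tempting, and the documents support none of them:

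- *The triggering event goes unrecorded.* It does not; Sections 15.2 and 16 require documentation.
- *Further follow-up is forbidden.* It is only not required.
- *About half of the planned safety observation is lost at a Month 3 discontinuation.* No contact is scheduled between Months 3 and 6, so the loss is one visit plus between-visit reporting.
- *Efficacy would be inflated.* Nothing in the documents links the course of an adverse event to lift, so no direction can be given.

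**Conclusion.** The point holds as an unreconciled rule on data collection, and it should be fixed. Taken literally, Sections 16 and 15.2 do not require later changes in severity, new events, the outcome, or the remaining scheduled assessments in subjects with persistent or worsening events. Section 7.4 and the safety endpoint analysis in Section 6 presume that follow-up data exist.

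For a discontinuation at Month 3, the loss is one scheduled visit, between-visit reporting and the ratings made only at Month 6. Each subject affected is at least 6.7% of those treated.

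The conclusion rests on reading discontinuation as exit, so confidence is moderate. The number of subjects affected and the direction of any efficacy bias are unknown. No view is taken on whether the discontinuation rule is clinically right.

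**What to change.** Reconcile Sections 7.4, 7.5, 15.2 and 16 on data collection, and define exit. State that discontinuation under Section 16 does not by itself end adverse event collection, or the scheduled Month 3 and Month 6 safety and non-invasive imaging assessments, unless the subject withdraws consent. Leave clinical handling of the event, and the biopsies, to the investigator.

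In the analysis text, state that safety is summarised in all treated subjects, and that the number of missing Month 6 assessments is reported with reasons.

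The cost is a few sentences of protocol wording, plus visits already on the schedule for the few subjects who would otherwise have left. The downside is the burden of those visits and possibly less favourable reported adverse event outcomes.

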## 17. Protocol Deviations

Emergency deviations (deviation necessary to avoid immediate apparent harm or protect life or physical well-being of subjects or others) and major deviations as defined by the reviewing IRB will be reported to the IRB within 5 working days of occurrence. All deviations will be tracked and summarized in the progress report for the next continuing IRB review.

## 18. Sources of Research Material

Demographics and medical history will include age, gender, weight, height, BMI, skin type, recent sun exposure, allergies, current medications, major illnesses, photographs, adverse events and treatment. Additionally, OCT images, ultrasound images, TEWL measurements, BTC 2000 measurements, and biopsies will be obtained.

High resolution ultrasound will be used to assess skin thickness and density. The standard time for use of high-resolution ultrasound should take approximately 5 minutes.

Transepidermal water loss (TEWL) measurements will be used to evaluate barrier function of the skin epidermal layer to determine progress of epidermal healing after treatment. The standard time for TEWL measurements should take approximately 5 minutes. Optical coherence tomography (OCT) will be used to noninvasively gather topographical and histologic images of pre- and post-treated skin. The standard time for OCT should take approximately 5-10 minutes. The BTC 2000 will be used to measure skin laxity, viscoelastic deformation, stiffness, energy absorption, elasticity, and deformation values of skin. The standard time for BTC 2000 should take approximately 5 minutes.

[figure not shown]
Biopsies will be taken using 0.33mm biopsy punches of the submental area. Biopsies will allow investigators to correlate changes seen in skin measurements with histology and gene expression. Time for two biopsies will take approximately five minutes. Biopsies for histology will be fixed immediately after collection in 4% PFA followed by paraffin embedding. Biopsies for gene expression will be put in RNA-Later solution and transferred to the Plastic Surgery Research Lab for gene expression analysis. Whole genome sequencing will not be performed, we will only be analyzing proteins and RNA expression related to collagen, elastin, and the extracellular matrix production.

